SPM	Smartpill Motility Monitoring System
UM	User Manual

3. Introduction

Gastroparesis is a common gastro-intestinal disorder with a range of clinical manifestations including nausea, vomiting, bloating, postprandial fullness, early satiety, and abdominal discomfort in association with demonstrable delays in gastric emptying. Gastroparesis has profound impact on the lives of affected patients, impairing quality of life, and produces a significant health care burden, leading to extensive emergency department visits and inpatient stays.

A range of therapies has been proposed for use in gastroparesis to reduce symptoms and promote adequate nutrient intake. Determination of the rate of gastric emptying is commonly employed to facilitate the decision to prescribe one of these therapies for a gastroparesis patient with significant symptoms.

For many years, Gastric scintigraphy is the standard of clinical practice for diagnosis of gastroparesis. However, it has been apparent that this method has a number of serious drawbacks including variability in methods between clinical centers, the choice of meal for clinical assessment, timing of image acquisition from scintigraphy, which call into question its validity to discriminate those with versus those without disease ; as a consequence, a standardized protocol has been advocated that employs a standard test meal with measurement of emptying in the late postprandial time period (4 hours) when most emptying is complete in healthy controls (Guidelines published by both the American Neurogastroenterology and Motility Society and the Society of Nuclear Medicine) but - to date - a small minority of medical centers in the United States have adopted this protocol. Additional drawbacks of gastric scintigraphy include the requirements to have access to a qualified nuclear medicine department and the potential for radiation exposure to individuals who may already have undergone extensive radiographic testing.

Because of the well-documented deficiencies of gastric scintigraphy, other methods for determination of gastric emptying have been proposed (e.g. Breath testing after consumption of different meals labeled with a non-radioactive isotope (^{13}C) (16, 17)), but such methods have also

some limits.

The SmartPill Motility Monitoring System (SPM) employs an ingested capsule that measures pH and pressure activity within the gastrointestinal lumen. The SPM gastric emptying time (GET) is determined when the capsule pH increases at least 2 units from the acidic environment of the stomach to the more neutral proximal duodenum. Some data comparing SMP vs gastric scintigraphy in healthy patients and in patients with established gastroparesis have recently been published with good performance and excellent safety results.

As a consequence of this trial, the SPM system was approved by the United States Food and Drug Administration (FDA) in July 2006 for determination of delayed gastric emptying and for measurement of whole gut transit, even if concerns have been raised by clinicians and insurance providers in response to this initial clinical trial that mandate additional investigation (related to small sample size, targeted population and gastric empty-time cutoff considered in this trial).

In this context, this trial is designed to study the intended population in which the device will be used, subjects with suspected gastroparesis based on their self-reported symptom profile. The study will compare patient management decisions based on results of gastric emptying scintigraphy tests to decisions based on SmartPill Motility Monitoring System study to assess both impact on patient management and diagnostic gain associated with the latter test.

4. Study Objectives and Endpoints

The study population consists of patients with symptoms of gastroparesis.

a. Primary objective

To evaluate per-device agreement in the diagnosis of delayed gastric emptying between SmartPill Motility Monitoring System (SPM) gastric emptying time (GET >5 hours) and the non-reference standard gastric scintigraphy test (>10% retention of a solid meal at 4 hours) in patients with symptoms of gastroparesis.

b. Secondary objectives

Several secondary hypotheses can be tested from data generated by this investigation which include but are not exclusive to:

1. To assess the device agreement of SPM with GES for detection of severe gastroparesis
Hypothesis: Severe gastric delay identified with scintigraphy (>35% at 4 hours) (35) is associated with severe prolongation of SPM GET (>8 hours) and impaired contractility (36)
2. To assess the correlation of gastroparetic symptoms measured by the PAGI-SYM symptom survey and PAGI-QUL survey instruments with SPM transit and fed response contractility parameters and with gastric emptying scintigraphy. *Hypothesis:* Gastroparetic symptoms correlate with discrete SPM measures
3. To quantify the additional abnormal motility (diagnostic gain) detected with SPM relative to GES. *Hypothesis:* The GI transit and contractility measures provided with SPM result in additional abnormal motility findings (diagnostic gain) over the conventional test gastric emptying scintigraphy in the symptomatic gastroparetic population
4. To assess the impact of the diagnostic gain associated with SPM on patient management
Hypothesis: The diagnostic gain realized with SPM results impact patient management decisions.

Study Endpoints

1. Primary Endpoint

Per patient device agreement for the diagnosis of delayed gastric emptying between SmartPill Motility Monitoring System (SPM) gastric emptying time (GET >5 hours) (18) and

the non-reference standard, gastric Emptying scintigraphy test (>10% retention of a solid meal at 4 hours)(13) in patients with symptoms of gastroparesis

2. Secondary Endpoints

2.1. Agreement between Gastric emptying time of smartpill capsule (GET>8hrs= severe) and gastroduodenal contractility and percent of radiolabeled meal retained at 4 hours on scintigraphy (>35% = severe)

2.2. Correlation between total GCSI scores, GCSI subscale scores for nausea/vomiting, postprandial fullness/early satiety, bloating , PAGA-SYM score for upper abdominal pain, PAGA-QOL score and SPM GET, SPM SBTT, SPM CTT, SPM fed response gastroduodenal contractility (frequency and AUC) and percent retention of radiolabeled meal measured with scintigraphic camera at 4 hours,

2.3. Number of abnormal SPM GET, SBTT,CTT and antroduodenal contractility findings (contraction frequency and AUC) and number of abnormal radiolabeled meal emptying findings measured with scintigraphic camera.

2.4. Documented patient management plans recording therapy, Dx tests, nutrition, and surgery decisions based on SPM results and based on GES and assessment of patient management change in accordance with following guidelines:

a. Change in Therapy: A change in category of drug therapy or the addition of a new category of drug therapy constitutes a change in management. Thus a change in treatment from prokinetic to antiemetic, neuromodulator or laxative category constitutes a change in patient management. A change of therapy within category such as switching from one prokinetic drug to another prokinetic drug does not constitute a change in patient management unless the drug is intended to impact a different GI region.

b. Dietary guidelines: Changes to diet constituting a change in patient management include: recommendation of diets specific for gastroparesis, recommendation of a liquid diet, initiation of TPN or G or J feeding tube.

c. Surgery: Relocation of feeding tube to new location (G tube changed to J Tube) constitutes change in management but not relocation of G tube to new gastric location. Either initiation or elimination of surgical referral constitutes change in management.

d. Diagnostic Testing: Any avoidance or additional diagnostic testing related to patient GI symptoms whether to detect abnormal motility or rule out alarm conditions constitute a change in management.

5. Investigation Plan

This is a multi-center, prospective study which aims to evaluate positive and negative device agreement in the diagnosis of delayed gastric emptying between SPM system gastric emptying time (GET >5 hours) and the non-reference standard gastric emptying scintigraphy test (>10% retention of a solid meal at 4 hours) in patients with symptoms of gastroparesis.

The study will include approximately 275 patients with symptoms of gastroparesis aged 18-80 years, who have no evidence of metabolic and/or organic disease.

Each subject will go through a Gastric scintigraphy test concurrently conducted with SPM testing after an overnight fast. The subject will be instructed to maintain a diary of times of meal consumption, bowel movements, and sleep.

Patient and physician will complete survey instruments (detailed in section 7 of protocol).

Subject will return the SPM receiver 5+2 days after ingestion day.

Physician will complete 4 management plans:

- Between 5-28 days (visit 4) after SPM and gastric scintigraphy test day- 3 management plans based first on one motility test blinded to the second test and then independently based on second test but not blinded to the first test result. The PI will then develop a third patient management plan based on both test results. This plan will be presented to the patient at the follow-up visit (visit 4)

Subjects will be contacted at 3 and 6 months post SPM procedure for follow-up assessment of symptoms.

Subjects will be compensated for completing the study.

All observations/ assessments to be conducted are displayed in the Trial Flow Chart (Appendix- A of Protocol) and detailed in the sections below

Study Duration: each subject is expected to participate in the study for two to five weeks (including medication wash) and up to 6 months follow up. Each subject will report to the study site for at least 4 visits and up to 6 visits.

Up to 16 months will be required to enroll 275 patients following IRB approval of the study. The completion of the study will require 20 months due to data collection and validation, data analysis, and the final clinical report.

Inclusion criteria

- Males and females between ages of 18-80 years of age with symptoms of gastroparesis for at least 12 weeks.
- Presenting with 2 or more of the following symptoms or signs which, in the opinion of the site investigator, are suggestive of a diagnosis of gastroparesis:
 - .1 Nausea, vomiting, or retching (dry heaves)
 - .2 Postprandial fullness or early satiety
 - .3 Bloating or visible abdominal distention
 - .4 Postprandial discomfort or pain
- Ability to stop proton pump inhibitors for 7 days and histamine₂ receptor antagonists, prokinetic agents, narcotic agents, anticholinergic drugs, and cannabinoids 3 days prior to SPM and gastric scintigraphy testing.
- No evidence of metabolic disease (hypothyroidism, uncontrolled diabetes [hemoglobin A1c >10% within the past 6 months], electrolyte imbalance).
- An upper endoscopy or upper gastrointestinal barium series within the past 2 years showing no organic disease that is potentially causative of symptoms.
- High probability of compliance and completion of study.

Exclusion criteria

- Participation in previous SmartPill clinical trials.
- Previous history of bezoars (the presence of retained liquid, bile, or small amounts of poorly organized food residue is permitted).
- Dysphagia to solid food or pills.
- Prior surgery involving the luminal gastrointestinal tract (cholecystectomy, appendectomy, and hysterectomy are permitted if performed > 3 months prior to SPM test).
- Any abdominal or pelvic surgery within the past 3 months
- Known or history of inflammatory bowel disease.
- History of diverticulitis, diverticular stricture, and other intestinal strictures.
- Chronic daily use of nonsteroidal anti-inflammatory drugs (ibuprofen, naproxen, etc.)
- Tobacco or alcohol use within eight hours prior to capsule ingestion.
- BMI > 40 kg/m².
- Allergies to eggs, bread, or jam.
- Females of childbearing age who are not practicing birth control and/or are pregnant or lactating. (Urine pregnancy testing will be performed on female subjects of child-bearing potential prior to capsule ingestion and gastric scintigraphy).
- Use of cardiac medical devices such as pacemakers and defibrillators (gastric stimulators, bladder stimulators, spinal stimulators, medication infusion devices, insulin pumps, continuous glucose monitors are permitted).
- Uncontrolled diabetes with a hemoglobin A1c >10%.
- Patient is expected to undergo MRI examination within 7 days after ingestion of the capsule

Prohibited Medications

Medications Which May Alter Gastric pH:

- (i) Proton pump inhibitors (omeprazole, lansoprazole, esomeprazole, dexlansoprazole, pantoprazole, rabeprazole) for 7 days prior to study including the day of SPM ingestion.

- (ii) Histamine₂ receptor antagonists (cimetidine, ranitidine, famotidine, nizatidine) for 3 days prior to study including the day of SPM ingestion.
- (iii) Antacids (containing magnesium, aluminium, or calcium carbonate) for 1 day prior to study including the day of SPM ingestion.

Medications That May Affect Gastrointestinal Motility: The following medications must be discontinued for 3 days prior to study including the day of SPM ingestion (if subject develops nausea to the degree that study discontinuation is contemplated, he or she may take promethazine, prochlorperazine, or ondansetron as rescue antiemetics in doses recommended by the site investigator):

- (i) Prokinetic agents (metoclopramide, domperidone, erythromycin, azithromycin, bethanechol, pyridostigmine)
- (ii) Narcotic analgesics (codeine, hydrocodone, oxycodone, methadone, fentanyl, etc.)
- (iii) Anticholinergic agents (dicyclomine, hyoscyamine, scopolamine)
- (iv) Cannabinoids (dronabinol, marijuana)

Permitted Medications

Prescription medications for maintenance of stabilized conditions (e.g., hyperlipidemia, thyroid disease, chronic anxiety or depression, birth control, etc.) are permitted if the condition and the dose are stable for three months prior to study participation.

6. Determination of Sample Size

In that accurate assessment of PPA · and NPA · is of utmost importance in this study, the sample size of 275 is based on the expected precision associated with our estimates expressed in terms of confidence interval width and 10% additional patients in order to compensate for 1 interim analysis performed. It is expected that 10% of data will be lost to follow-up or not evaluable resulting in an effective sample size of approximately 248. The precision associated with each estimate is a function of the true unknown

value of the parameter being estimated, and the percentage of delayed diagnoses by the predicate in the case of positive percent agreement and the percentage of negative diagnoses by the predicate in the case of negative percent agreement. For the purpose of our calculations of the expected confidence interval half width, it is assumed that 40% of patients will be delayed by the predicate. A range of possible scenarios for the true value of the parameter were considered for PPA and NPA and calculations of the expected interval half width appear in the table below:

True value	50%	60%	70%	80%	90%
PPA	10.3	10.1	9.5	8.3	6.2

Note that a true value for π_{PPA} or π_{NPA} of 50% represents the worst-case scenario with regards to precision and therefore may be taken as an upper bound of expected accuracy. Calculations reveal that both confidence intervals will have a half width of at most 9.8

7. Statistical Methods

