7.1.2. Clinical Investigation Plan (CIP) Deviations

Any deviation from specified statistical plan will be in addition to “per protocol” analysis and will be reported as such. Post-hoc analysis will be conducted according to the existing data gathered, if necessary.

Full-list of protocol deviations will be provided in a separate file; protocol deviations to be excluded from PPAS1 and PPAS2 (refer to section 7.1.3) will be discussed and validated with the study team prior to run statistical analysis.

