7.1.3. Analysis Sets

Two analysis sets will be created for study purpose:

1. Full Analysis Set (FAS). FAS includes all enrolled subjects:

- who signed the informed consent and
- who satisfied to the eligibility criteria

FAS will be used for subjects disposition, population description, and for Safety analysis.

2. Per Protocol Analysis set (PPAS): PPAS is a subset of the FAS, restricted to subjects who adhere to the protocol, in terms of SPM and Scintigraphy procedures, and minimal follow-up.

Two subsets of the PPAS - according to follow-up- will be created and used for Performance analysis purpose:

- PPAS1: Subjects who completed the full study follow up to 6 months FU
- PPAS2: Subjects who completed visit 4 with 3 patient management plans- this group will be larger than the above and will have all data for study end points, even though not completed full study flow.

Listing of major protocol deviations to be excluded from the PPAS1 and 2 will be provided by the study team prior to run statistical analysis.

Per protocol Analysis Sets (PPAS1 and PPAS2) will be used for Performance analyses.

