3. The relative frequency will be computed for SPM transit and contractility results that provide diagnostic gain (additional abnormal motility findings) compared to conventional test results. A corresponding 95 percent confidence interval will also be provided.

4. The percent of changes to patient management plans will be estimated. Frequencies of the types of changes will be summarize and presented in tabular form.

Secondary performance endpoints will be run on both PPAS1 and PPAS2.

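### As the SAP states it, motility drugs are withheld only through ingestion day, while SBTT and especially CTT can be recorded later, and secondary analyses 2 and 3 make no use of the medication data

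*SAP*

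**What the plan says.** **Drug window.** Section 5, Prohibited Medications, names four groups that may affect motility: prokinetics, narcotic analgesics, anticholinergics and cannabinoids. Its rule is "The following medications must be discontinued for 3 days prior to study including the day of SPM ingestion". Three rescue antiemetics are allowed for severe nausea. The inclusion criteria give the same 3 days before testing. Neither place mentions the days after ingestion.

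**Recording period.** The SAP gives no transit duration, but two statements show that it expects the capsule to be in use or in the body for days. Section 5 says "Subject will return the SPM receiver 5+2 days after ingestion day", and one exclusion criterion reads "Patient is expected to undergo MRI examination within 7 days after ingestion of the capsule".

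**Use of the data.** Endpoint 2.3 in Section 4 begins "Number of abnormal SPM GET, SBTT,CTT and antroduodenal contractility findings" and sets these beside abnormal scintigraphy findings. In Section 7.9, item 2 correlates symptom and quality-of-life scores with GET, SBTT and CTT. Item 3 gives the relative frequency of additional abnormal SPM findings with a 95% interval. On the analysis set: "Secondary performance endpoints will be run on both PPAS1 and PPAS2".

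**Analysis sets and medication data.** Section 7.1.3 describes the per-protocol set as "restricted to subjects who adhere to the protocol, in terms of SPM and Scintigraphy procedures", plus minimal follow-up. Section 7.1.2 leaves the "protocol deviations to be excluded from PPAS1 and PPAS2" to discussion with the study team before analysis. Section 7.7 plans a yes/no medication summary at baseline and each follow-up, and a listing of details by visit.

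**The concern.** Diagnostic gain is a comparison. Scintigraphy ends at 4 hours on the test day, inside the drug-free window. SBTT (when gastric exit is late) and CTT can be recorded outside it. The SAP itself treats the listed drugs as able to alter motility. An opioid or anticholinergic restarted the next day could add an abnormal CTT that scintigraphy had no chance to show, and this would count as gain. A prokinetic could hide a real delay. The symptom correlations with SBTT and CTT are open to the same influence.

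At stake is what the secondary results can claim about small-bowel and colonic dysmotility. A reader could find drug use in the Section 7.7 listings, but no planned result connects it to SBTT or CTT.

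**Working it through.** **Text set side by side**

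| Element | Where | Timing or handling |
|---|---|---|
| Motility drugs withheld | Section 5, Prohibited Medications | 3 days before, through ingestion day |
| Scintigraphy reading | Section 4, primary endpoint | 4 hours, ingestion day |
| Primary SPM cut-off | Section 4, primary endpoint | GET above 5 hours, reached on ingestion day |
| Receiver return | Section 5 | 5+2 days after ingestion |
| SBTT, CTT in correlations and gain | Section 7.9, items 2 and 3 | no medication exclusion, stratification or sensitivity analysis |
| Medication data | Section 7.7 | summary and listing only |

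Both primary classifications are settled on ingestion day, so PPA and NPA do not depend on drugs resumed later. SBTT and CTT can.

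**How many subjects would matter**

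The SAP gives no rate of drug use after ingestion and no rate of abnormal CTT, so the bias itself cannot be estimated. What can be computed is a tipping point: the net number of subjects whose CTT classification would have to change for the percentage abnormal to move by more than its 95% half width.

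Inputs: 167 enrolled (Section 7.12) and the 10% loss of Section 6, assumed to apply here as well. Evaluable: 167 × 0.90 = 150.3, about 150. One subject is 1/150 = 0.67 points. Half widths are Clopper-Pearson, the method the SAP names for the primary analysis.

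| Abnormal CTT (assumed) | Half width, n = 150 | Largest net change within it | Smallest net change beyond it |
|---|---|---|---|
| 10% (15/150) | 5.1 points | 7 (4.7 points) | 8 (5.3 points) |
| 20% (30/150) | 6.7 points | 10 (6.67 against 6.69 points) | 11 (7.3 points) |
| 30% (45/150) | 7.6 points | 11 (7.3 points) | 12 (8.0 points) |
| 50% (75/150) | 8.3 points | 12 (8.0 points) | 13 (8.7 points) |

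If 10%, 20% or 30% of subjects resume a listed drug (assumed: 15, 30 or 45 of 150), the net share of them that must be reclassified is:

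- for 8 subjects: 8/15 = 53%, 8/30 = 27%, 8/45 = 18%;
- for 13 subjects: 13/15 = 87%, 13/30 = 43%, 13/45 = 29%.

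At low exposure, more than half of the exposed subjects would have to change class, all net in one direction. At high exposure the required share is more modest. If gain is counted per subject, total gain moves by no more than the CTT percentage, because subjects abnormal on another SPM measure already count.

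**Precision of a sensitivity analysis**

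If 10% to 30% are excluded (assumed), 135 to 105 of 150 remain.

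- Item 3, worst case near 50%: 75/150 gives 41.7 to 58.3 (half width 8.3); 68/135 gives 41.6 to 59.1 (8.7); 52/105 gives 39.6 to 59.5 (9.9).
- Item 2, correlation near zero, Fisher z approximation tanh(1.96/√(n−3)): 0.160 at n = 150, 0.169 at n = 135, 0.192 at n = 105. The SAP plans bootstrap intervals, so these are only indicative.

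**The case against.** **The protocol may settle it.** How long a drug is withheld is a protocol matter, Section 5 of the SAP is a summary, and the protocol is not at hand. This stands as a limit: if the protocol carries the restriction to capsule exit, the point largely falls away. But the SAP writes out a medication rule with an end point, and its own Section 7.9 does not use the medication data.

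**A stronger reading of the analysis sets.** A reader might infer that PPAS1 and PPAS2 are bound to keep subjects who resume these drugs, since the SAP states no rule that they would break. The document does not support that. The per-protocol set follows adherence to the protocol, and the deviation list is still to be fixed. Whether such subjects stay in is open.

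**The analyses are descriptive and partly covered.** No decision rule rests on items 2 and 3, Section 7.7 lists medication, Section 7.1.2 allows post-hoc analysis, and endpoint 2.3 already names the measures one by one. This is fair, and it keeps the point small. It does not supply a planned result that relates drug use to SBTT or CTT.

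**A broad exclusion could do harm.** Laxatives are not on the prohibited list, and patients may take them because colonic transit is slow, so excluding users could remove true delay. Rescue antiemetics are expressly permitted. This stands, and the exclusion should be limited to the listed drugs.

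**Dates may be missing.** Section 7.7 lists by visit, and subjects are told to "maintain a diary of times of meal consumption, bowel movements, and sleep", not drug intake. Some subjects may be unclassifiable. This also stands.

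**Conclusion.** The point holds within the SAP's text: the stated drug window closes before SBTT and CTT need be complete, and items 2 and 3 of Section 7.9 use both measures without reference to drugs taken in between. Part of the diagnostic gain or of the symptom correlations could therefore be a drug effect.

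Its size and direction are unknown. The threshold of 8 to 13 net reclassified subjects rests on assumed abnormal-CTT rates of 10% to 50% and on about 150 evaluable subjects. A large distortion is implausible if few subjects resume a listed drug and possible only if many do. A reader might also take this as doubt about the primary agreement result. It is not, because that result is read on ingestion day. The point qualifies secondary conclusions about transit beyond the stomach and merits a modest addition to the plan.

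**What to change.** 1. Keep the all-subject analyses of Section 7.9 items 2 and 3 as the main result.
2. Report diagnostic gain from SBTT and CTT separately from gain from GET and gastroduodenal contractility.
3. Where recorded dates allow, add one sensitivity analysis of items 2 and 3 that excludes only subjects who took a prokinetic, narcotic, anticholinergic or cannabinoid between ingestion and capsule exit. Report how many were exposed and how many could not be classified.
4. Do not exclude users of laxatives or permitted rescue antiemetics; report their numbers descriptively.
5. If the protocol restricts the listed drugs after ingestion, cite that rule and put breaches on the deviation list for PPAS1 and PPAS2 instead of steps 3 and 4.

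The cost is SAP wording, one classification from details already due to be listed, and one repeat of two secondary analyses. Enrolment has stopped, so the drug window itself can hardly be changed for subjects already tested. There are three downsides. Intervals widen slightly: the worst-case half width for item 3 is 8.7 to 9.9 points instead of 8.3 if 10% to 30% are excluded, and for item 2 about 0.17 to 0.19 instead of 0.16. Some subjects will be unclassifiable. Subjects who resume drugs may be sicker, so a difference may reflect selection as well as drug effect. It should qualify the SBTT/CTT conclusion, not replace it.

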7.8. Interim Analyses

One (partial) interim analysis Interim analyses has already been performed (June 2015) on primary endpoint, on N=130 patients. Final analysis will occur on 167 enrolled at the end of the study.

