7.9. Evaluation of Objectives

III.2 Primary analysis

Since a clearly defined universally accepted physiological definition of disease in this population does not exist, the diagnostic test under evaluation (SPM GET) will be compared to a non-reference standard test method, the percent retention of a radiolabelled solid meal at 4 hours on gastric scintiscanning. Device agreement will be examined through use of the positive percent agreement (PPA) and negative percent agreement (NPA). (38), the Statistical Evaluation of

Medical Tests for Classification and Prediction. Oxford University Press Inc, New York. Let π_{PPA} represent the true positive percent agreement defined as the probability of a positive SPM test result given the non-reference is positive and let π_{NPA} represent the probability of a negative SPM test result given the non-reference is negative. The primary analyses of this trial is estimation of these parameters in order to assess the equivalence between the diagnostic test under evaluation and the non-reference standard. Maximum likelihood estimates of π_{PPA} and π_{NPA} will be computed based on collected data i.e., conditional relative frequencies in addition to corresponding 95% confidence intervals based on the methodology of Clopper and Pearson (28). Additional measures such as estimates of the overall percent agreement and Cohen's kappa will be calculated.

Primary endpoint analysis will be run on PPAS1 and PPAS2.

III.2 Secondary analyses

1. The correlation between diagnoses of profound gastric retention on scintigraphy (>35% at 4 hours) with severe prolongation of SPM GET (>8 hours) and impaired contractility will be examined using relative frequencies. 95% confidence intervals will also be provided.
2. Total GCSI scores as well as GCSI nausea/vomiting, GCSI postprandial fullness/early satiety, and GCSI bloating subscale scores, PAGI-SYM upper abdominal pain scores and PAGI-QOL scores will be correlated with SPM GET, SPM SBTT, SPM CTT scintigraphy gastric retention at 4 hours and SPM gastroduodenal and fed response contractility profiles. Since validity of the standard confidence interval corresponding to the Pearson correlation requires distributional assumption which will not be met based on the nature of the data to be collected, bootstrap methodologies will be utilized alternatively to construct said intervals.

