7.12. Changes to Planned Analysis

Per protocol, final statistical analysis was scheduled once N=275 patients were enrolled and completed the study ; due to sponsor decision upon interim analysis primary endpoint results, decision have been taken to early stop the enrollment at N=167 subjects. So, final statistical analysis will be run on N=167 enrolled subjects.

8. Validation Requirements

Original Statistical Programmer performs a visual inspection of the code and output to confirm functionality (Level III as per 056-Wi 181).

9. References

2. De La Loge C, Trudeau E, Marquis P et al. Responsiveness and interpretation of a quality of life questionnaire specific to upper gastrointestinal disorders. Clin Gastroenterol Hepatol. 2004 Sep;2(9):778-86.

10. Statistical Appendices

N/A

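### SAP Section 6 caps both half widths at 9.8, but its own PPA row shows 10.3 and 10.1, and precision is never restated for the 167 patients finally enrolled

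*SAP*

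**What the plan says.** Section 6 (Determination of Sample Size) sets 275 patients on the basis of confidence interval width, including a 10% addition for one interim analysis. On losses it says: "It is expected that 10% of data will be lost to follow-up or not evaluable resulting in an effective sample size of approximately 248". It assumes that scintigraphy classes 40% of patients as delayed, and says that "calculations of the expected interval half width appear in the table below". The PPA row reads 10.3, 10.1, 9.5, 8.3 and 6.2 for true values of 50, 60, 70, 80 and 90%. The text then notes that a true value "of 50% represents the worst-case scenario with regards to precision and therefore may be taken as an upper bound of expected accuracy", and closes with "Calculations reveal that both confidence intervals will have a half width of at most 9.8".

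Section 7.9 plans "corresponding 95% confidence intervals based on the methodology of Clopper and Pearson" for PPA and NPA, and adds: "Primary endpoint analysis will be run on PPAS1 and PPAS2".

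The sample size has since changed. Section 7.8 says "Final analysis will occur on 167 enrolled at the end of the study", and Section 7.12, after recording the early stop, says "final statistical analysis will be run on N=167 enrolled subjects". Neither section gives an expected half width for that number.

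**The concern.** The contradiction can be seen without calculation. Section 6 names 50% as the worst case, tabulates 10.3 there, and then states a maximum of 9.8. The 60% entry of 10.1 also exceeds it.

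Three further questions follow: which sample size each figure rests on, whether either matches the exact interval that will be reported, and whether the statement still describes the trial now that enrolment has stopped at 167.

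Apart from the 10% added for the interim analysis, expected precision is the whole rationale that Section 6 offers for the sample size. The primary analysis is estimation of PPA and NPA, so half width is the design property that tells a reader what the trial can deliver. A reader who takes 9.8 at face value would expect a tighter PPA interval than the design gives, and a clearly tighter one than 167 patients can give.

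**Working it through.** **Inputs.** From Section 6: 275 planned, 10% loss, 40% delayed. From Section 7.9: two-sided 95% Clopper-Pearson intervals. From Sections 7.8 and 7.12: 167 enrolled.

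- Planned: 275 × 0.9 = 247.5, about 248. Delayed 248 × 0.4 = 99.2; not delayed 148.8.
- Final, no loss: 167 × 0.4 = 66.8, so 67 delayed and 100 not.
- Final, 10% loss: 167 × 0.9 = 150.3, about 150, so 60 delayed and 90 not.

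**Step 1: reproduce the SAP's figures.** Section 6 names no formula. The Wald half width in percentage points is 196 × √(p(1−p)/n).

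| True value | 50% | 60% | 70% | 80% | 90% |
|---|---|---|---|---|---|
| SAP, PPA row | 10.3 | 10.1 | 9.5 | 8.3 | 6.2 |
| Wald, n = 99.2 (N = 248) | 9.84 | 9.64 | 9.02 | 7.87 | 5.90 |
| Wald, n = 90 (N = 225) | 10.33 | 10.12 | 9.47 | 8.26 | 6.20 |

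The 9.8 is the Wald worst case at the stated 248. All five cells of the row match Wald at 90 delayed patients, that is, 225 evaluable at 40%. Since 225 = 250 × 0.9 and 275 = 250 × 1.10, the row may predate the 10% interim addition. That origin is inferred. The mismatch with 248 is not.

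**Step 2: use the planned interval.** The expected Clopper-Pearson half width is the sum over x of Binomial(x; n, p) × (upper − lower)/2.

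| True value | 50% | 60% | 70% | 80% | 90% |
|---|---|---|---|---|---|
| PPA, n = 99 | 10.2 | 10.0 | 9.4 | 8.2 | 6.3 |
| NPA, n = 149 | 8.3 | 8.1 | 7.6 | 6.7 | 5.1 |

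At the planned 248 the bound of 9.8 therefore fails for PPA, by about 0.4, and holds for NPA. Clopper-Pearson does not reproduce the printed row at any n from 85 to 111. The nearest is n = 97, which matches four cells but gives 6.4 at 90% where the row has 6.2.

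**Step 3: the final sample size.** Expected Clopper-Pearson half widths:

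| True value | 50% | 60% | 70% | 80% | 90% |
|---|---|---|---|---|---|
| PPA, all 167 evaluable (n = 67) | 12.4 | 12.2 | 11.4 | 10.1 | 7.7 |
| NPA, all 167 evaluable (n = 100) | 10.1 | 9.9 | 9.3 | 8.2 | 6.3 |
| PPA, 150 evaluable (n = 60) | 13.1 | 12.8 | 12.1 | 10.6 | 8.2 |
| NPA, 150 evaluable (n = 90) | 10.7 | 10.5 | 9.8 | 8.7 | 6.6 |

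Against 9.8, the worst case for PPA is 2.6 to 3.3 points wider (12.4 − 9.8; 13.1 − 9.8) and for NPA 0.3 to 0.9 wider (10.1 − 9.8; 10.7 − 9.8). The no-loss case is the most favourable, because Section 7.1.3 defines PPAS1 and PPAS2 as subsets of the enrolled patients.

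**Step 4: sensitivity to the delayed share.** This range is an assumption. With 150 evaluable and a true value of 50%, PPA is 15.1 if 30% are delayed (n = 45) and 11.7 if 50% are (n = 75).

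**The case against.** The best defence is that little depends on this sentence. The documented contradiction is half a point (10.3 against 9.8), for a target that has been abandoned. No decision rule uses 9.8, and the reported intervals will show the actual width. All of that stands, and it limits the consequence.

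It can also be said that planning with a normal approximation and analysing with an exact interval is not in itself an error, and that Wald is only inferred here. Both are fair. Every printed PPA cell is moreover within about 0.1 of the exact value for the planned 248, so for that plan the row is adequate in practice. It is the 9.8 sentence that misleads. This narrows the point but does not remove it, because the sentence still disagrees with the row and with the planned interval.

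Finally, the 167 is openly disclosed, and nothing says that 9.8 applies to it. Most of the excess at 167 comes from the early stop and only about 0.4 points of the PPA excess from the bound itself. That attribution is right. Even so, Section 6 is the SAP's only statement of precision, and it describes a sample that the same document says will not be analysed.

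**Conclusion.** The point holds. As written, the 9.8 bound is contradicted by the PPA row beside it, and it fails for PPA under the planned Clopper-Pearson interval even at 248 evaluable patients (10.2). NPA meets it at that size (8.3). At the final 167 enrolled, neither parameter meets it in the worst case: PPA is 12.4 to 13.1 and NPA 10.1 to 10.7. The NPA excess with no loss is slight and depends on the exact method, since Wald at n = 100 gives 9.8.

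The figures at 167 carry over the SAP's 40% delayed share and 0 to 10% loss. The SAP does not give the actual sizes of PPAS1 and PPAS2. The contradiction itself needs no assumption. The error is in the stated planning basis; it biases no estimate and changes no planned analysis.

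**What to change.** In Section 6, delete the 9.8 statement and base all precision figures on one stated sample size and the Clopper-Pearson method. Replace the table with the PPA and NPA rows of Step 3 for the final sample size, stating the number assumed evaluable (150 after 10% loss, or 167 if none are lost) and the 40% delayed share. Say that 167 results from the sponsor's early stop described in Section 7.12 and was not derived from a precision target. If the 275-patient rationale is kept, mark it as history and correct its worst cases to 10.2 for PPA and 8.3 for NPA. Sections 7.8 and 7.12 can then refer to the restated figures.

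The cost is SAP wording only. The stated precision becomes less favourable; no patients are added and the analysis is unchanged.
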